Edited to use the term 'ileostomy' rather than 'ostomy' throughout the PICF	PICF	HREC request	27MAY21
The following statements were added to p. 4, point 6: "The size of each capsule is about 20 mm. If you would like to see what the capsule looks like, the study staff can show you an empty capsule at the screening visit."	PICF, p. 4	HREC request	27MAY21
"Therapeutic Goods of Australia [TGA]" was changed to "Australian Therapeutic Goods Administration [TGA]."	PICF, p. 2	HREC request	27MAY21
An explanation of LMN-201 was added to the section What is the purpose of this research? (p. 2): "To be effective, the capsules must deliver LMN-201, undamaged, to the end of the small intestine. This is where the LMN-201 components will be effective in treating C. difficile bacterial infection by specifically destroying the C. difficile bacteria and binding to the toxins produced by the C. difficile bacteria. This study will give the researchers information about if the LMN-201 components are still present at the end of the small intestine."	PICF, p. 2	HREC request	27MAY21
The following statement was added to point 4 on p. 3 and p. 4: "Women who are pregnant, planning to become pregnant, or are breastfeeding, cannot participate in this study"	PICF, p. 3 and 4	HREC request	27MAY21
The following statement was added to the Study Visit section: "You may start eating again 2 hours after administration of the study drug. You will be provided snacks and up to two meals during the study visit."	PICF, p. 3	HREC request	27MAY21
The following statement has been added above the text in bold in the "Pregnancies, Breastfeeding, and Birth Control Information" section: "It is highly recommended that you inform your partner of your participation in this study and	PICF, p. 7	HREC request	27MAY21

that highly effective methods of contraception (as detailed above) are strongly recommended."			
Opioid test was mistakenly included in the procedures done at the study visit. This was removed Study Visit Section. Opioid test will only be done at the screening visit	PICF, p. 4 and 5	Sponsor-initiated change	27MAY21

Table of Contents

PRINCIPAL INVESTIGATOR'S AGREEMENT	2
SPONSOR SIGNATURE	3
CONTACT INFORMATION	4
TABLE OF CONTENTS.....	7
1. PROTOCOL SUMMARY.....	9
1.1 Synopsis.....	9
2. LIST OF ABBREVIATIONS AND TERMS.....	13
3. INTRODUCTION.....	14
3.1 Background and Rationale.....	14
3.2 Risk/Benefit Assessment	15
4. OBJECTIVES AND ENDPOINTS	15

1. PROTOCOL SUMMARY

1.1 Synopsis

Study Title: Exploratory study to assess delivery of LMN-201 components via enteric capsules in the gut of individuals with ileostomies	
Study Number: CDI01	
Phase of development: Phase 1	
Investigational Product: Components of LMN-201 (a cocktail consisting of a bacteriophage lysin specific for C. difficile organism and three VHH-derived proteins that bind and inhibit C. difficile toxin B, delivered in whole, spray-dried spirulina (Arthrospira platensis) biomass)	
Sponsor: Lumen Bioscience, Inc.	
Principal Investigator (PI): [name]	
Study Center: Coral Sea Clinical Research Institute	
Study Objectives (Primary):	
 To determine if enteric capsules are sufficient to deliver LMN-201 therapeutic proteins (VHH proteins and lysin) to the terminal ileum.
Study Objectives (Exploratory):	
 To document the presence of LMN-201 therapeutic proteins at the terminal ileum To determine variability between individuals in the quantity of LMN-201 therapeutic proteins at the terminal ileum
Subject Population	Adults aged 19 and above with mature ileostomy
Study Design	
This is a Phase 1, multi-site, open label, exploratory study of LMN-201 to evaluate the function of enteric capsules on drug release.
 
Eligible volunteers with mature ileostomies will be enrolled and sequentially assigned to treatment. After documentation of informed consent, subjects will be asked to swallow 4 enteric capsules of LMN-201 components, 1 enteric capsule containing ring-shaped transit markers, and 1 immediate release capsule containing tube-shaped transit markers. Every hour following ingestion, ileostomy fluid will be collected, weighed, filtered, and analyzed. The procedure will be repeated for 4 hours after capsules and/or transit markers are observed in the collected ileostomy fluid, or 12 hours after ingestion, whichever time is shorter.
 
In the first cohort, participants will receive only one of the LMN-201 VHH proteins administered in 3 enteric capsules as well as 1 enteric capsule containing lysin, 1 enteric capsule containing ring-shaped transit markers, and 1 immediate release capsule containing tube-shaped transit markers. In the second cohort, participants will receive 1 enteric capsule of each of the LMN-201 VHH proteins as well as 1 enteric capsule containing lysin, 1 enteric

	
capsule containing ring-shaped transit markers, and 1 immediate release capsule containing tube-shaped transit markers.
 
The trial will be adapted between the first and the second cohort in the following manner:
 
 • If intact enteric capsules are observed in the ileostomy fluid of more than one participant 
 ○ And the transit time is less than 4 hours, then a fluid restriction to less than 150 ml per hour will be implemented for the second cohort. ○ And the transit time is greater than 4 hours, then immediate release capsules will be utilized for the second cohort. • If the number of enteric capsules that remain encapsulated in the ileostomy fluid is less than 20% 
 ○ Then the number of subjects in the second cohort will decrease from six to three.
Number of Subjects	Enrollment is planned for 2 cohorts of up to 6 subjects per cohort
Study Duration	Estimated time from when study opens to enrollment until completion of data analysis is 1-2 months.
Participant Duration	Each participant will complete the study in a single calendar day. The screening visit, to be completed up to 15 days prior to study visit, will take 1-2 hours.
Inclusion Criteria	
 • Adult (19 years of age or older) • Stable ileostomy (no revisions in the last 6 months) • Medically stable, but may be on medications for chronic conditions • Willing to participate in the clinical trial
Exclusion Criteria	
 • Individuals unable or unwilling to provide adequate informed consent • Non-English-speaking individuals • Clinically significant disease • Pregnancy, anticipated pregnancy, or breastfeeding • Use of anti-diarrheal medicine • Gastroparesis • Opioid use
Study Endpoints (Primary)	
 • Presence or absence of capsules and/or transit markers in ileostomy fluid by visual observation
Study Endpoints (Exploratory)	
 • Detect presence of LMN-201 therapeutic proteins (VHHs and lysin) in collected ileostomy fluid by EIA • Quantitate LMN-201 therapeutic proteins (VHHs and lysin) in collected ileostomy fluid by EIA

Safety and Tolerability Parameters	All dosed subjects will be evaluated for any safety and/or tolerability concerns
---	--

1.2 Schedule of Activities (SoA)

	Screening Visit	Study Visit		End of Study
		Dose	Follow up	
	Day -15 to 0	Hour 0	Hourly for 4 hours following observation of any transit markers or capsules, or for 12 hours, whichever time is shorter	
Study Procedures				
Consent	X			
Inclusion/exclusion criteria	X	X		
Medical History	X			
Physical Exam	X	X		
Vitals signs	X	X	X	
Urine Sample	X	X		
Study investigational product (IP) administered		X		
Collect ileostomy fluid for analysis ¹		X	X	
Record AEs			X	
Ship ileostomy fluid ¹				X

¹ See Manual of Procedures (MOP) for complete descriptions.

2. LIST OF ABBREVIATIONS AND TERMS

ADME	Absorption, Distribution, Metabolism, and Elimination
AE	Adverse event
CDI	C. difficile infection
CRF	Case report form
eCRF	Electronic case report form
EIA	Enzyme Immunoassay
GI	Gastrointestinal tract
cGMP	Current Good Manufacturing Practices
GRAS	Generally Regarded as Safe
ICF	Informed Consent Form
ICH	International Council for Harmonisation of Technical Requirements for Pharmaceuticals for Human Use
IEC	Independent Ethics Committee
IP	Investigational product
IRB	Institutional Review Board
MOP	Manual of Procedures
PI	Principal Investigator
SAE	Serious adverse event
US FDA	United States Food and Drug Administration
VHH	Binding domain fragment of a single-domain camelid antibody

3. INTRODUCTION

3.1 Background and Rationale

Targeted delivery of any therapeutic agent is the key consideration of efficacy. Typically, therapeutic agents are delivered by oral or injection pathways and are then subjected to Absorption, Distribution, Metabolism, and Elimination (ADME) effects. Each of these effects reduces the amount of active product able to be delivered to the site of action, thus reducing efficacy.

Lumen's solution to treat and prevent enteric diseases is to provide the drug directly to the site of action, bypassing ADME effects. Delivering the therapeutic biomolecule within a safe food product, for example, spirulina (*Arthrospira platensis*) biomass, that is not absorbed by the intestinal tract removes any loss of the active agent by gastric digestion.

Distribution concerns are thus fully eliminated as the product is delivered directly to the site of disease. With protein-based biomolecules, digestion of the therapeutic is the functional equivalent to metabolism within the gastrointestinal (GI) tract and remains the most significant challenge. Elimination, through the function of the GI tract, is linear and predictable. Most importantly, it does not reduce the amount of active agent at the site of action. Transit time, however, can affect the duration of action.

Severe *C. difficile* colitis is associated with significant morbidity and mortality worldwide (Balsells et al., 2019). It causes an inflammatory colitis that can lead to diarrhea, abdominal pain, fever, and malaise. The biomolecules Lumen Bioscience has developed to treat and prevent *C. difficile* infection (CDI) need to be delivered, undigested, and in a fully functional form to the distal small bowel and large intestine to be effective. LMN-201 in its final form will be a 'cocktail' of several prophylactic proteins of two distinct classes: a bacteriophage lysin, and several engineered binding domain fragments of a single-domain camelid antibody (VHHs) delivered orally within whole, spray-dried spirulina biomass. The spirulina-bioencapsulated therapeutic proteins are delivered in vegetable-based, enteric delivery capsules of 500 mg total spirulina biomass. Such capsules are designed to release the drug product at or before the terminal ileum, the earliest point in the GI tract where conditions, including CDI, become established in most patients. These capsules are commonly used and procured from an industry provider (Vcaps Enteric, Capsugel, a Lonza company) and are covered by an active Drug Master File with the United States Food and Drug Administration (US FDA).

The first class of LMN-201 contains a single representative: a bacteriophage-derived lytic enzyme that is highly specific for degrading the *C. difficile* cell wall resulting in rapid hypotonic death (Wang, et al., 2015). These lytic enzymes, also called 'endolysins' or simply 'lysins', are a class of cell wall hydrolases with a narrow spectrum of activity. Research by the Fischetti Lab at Rockefeller University has shown that these enzymes efficiently kill all clinical isolate *C. difficile* strains tested to date, while leaving commensal bacteria undisturbed.

The second class consists of several VHHs that neutralize *C. difficile* exotoxins. Prior research has shown toxin B to be the primary driver of the disease pathology (Carter et al., 2015). Lumen Bioscience has developed three distinct VHHs that target different epitopes of toxin B.

As discussed further in the Investigator's Brochure, the safety and efficacy of LMN-201's therapeutic proteins were evaluated in a series of *in vitro* and *in vivo* studies. *In silico* assessments of target epitope homology to human and commensal bacterial proteomes showed a low risk of cross-reactivity. The

efficacy of LMN-201 was successfully demonstrated in both mouse and hamster challenge models of CDI. These data strongly support the evaluation of LMN-201 in human subjects.

This is a preliminary study to determine if enteric capsules containing constituents of LMN-201 are sufficient to deliver therapeutic proteins to the terminal ileum.

3.2 Risk/Benefit Assessment

Spirulina has a well-established and documented safety profile, leading the US FDA to conclude that spirulina is Generally Regarded as Safe (GRAS) and requires no further toxicity studies. Possible non-serious adverse events (SAEs) have been reported with spirulina intended as a nutritional supplement. The US FDA MedWatch from January 2001 to July 2009 identified the most common non-SAEs from spirulina as: nausea; diarrhea; vomiting; fatigue; headache; dizziness; itching; rash, and abdominal cramps. These reports lacked information on the quantity, duration, individual history, or quality of spirulina used and were based on non-GMP spirulina (Marles et al., 2011).

VHH antibodies are too large for systemic absorption through the gut lining and are directed with high specificity at pathogen target epitopes, unlike anything in the human body. As a result, the risk of off-target toxicity in humans is close to zero. Lumen Bioscience completed a successful Phase 1 clinical trial in Australia in March 2020 with its initial VHH candidate, LMN-101. Systemic absorption of the engineered prophylactic protein was not detected, and there were no significant AEs.

Lytic enzymes have an excellent profile for an orally dosed anti-microbial targeted to organisms in the GI tract. Similar to VHHs, they are too large to be systemically absorbed, greatly reducing concerns of immunogenicity. Bacteriophages produce lytic enzymes that are ubiquitous in the human GI tract. At any given time, as many as 10^{12} bacteriophage are present in the human gut (Shkorporov et al., 2019). Humans are continuously exposed to lytic enzymes during normal microbiome activity with no known ill effects. An intravenous (IV)-infused *Staphylococcus aureus* specific lytic enzyme, CF-301, has been shown to be safe and effective in Phase 2 clinical trials (Fowler et al., 2020), further demonstrating the safety of this class of enzymes. Lysozyme, the canonical member of this enzyme family, is a broad spectrum bacteriolytic enzyme. It is approved for use in several countries, including Japan (Hashida, et al., 2002), and possesses various applications for oral administration as contemplated by Lumen Bioscience. The US FDA has concluded that lysins are also GRAS and has required no further toxicity studies from other companies producing oral lysin-containing products.

These safety records are consistent with the results generated by Lumen in a non-GLP safety study involving administration of LMN-201 to mice. No GLP studies or formal toxicology studies have been conducted with this product.

While participation may not offer direct medical benefit to subjects, an effective CDI preventative would offer a societal benefit. Considering the overall burden of the disease, the Sponsor considers the potential benefits of participation to exceed the risks.

4. OBJECTIVES AND ENDPOINTS

OBJECTIVES	ENDPOINTS
Primary	
To determine if enteric coating on components of LMN-201 is sufficient to deliver therapeutic proteins to the terminal ileum.	Presence or absence of capsules and/or transit markers in ileostomy fluid by visual observation

OBJECTIVES		ENDPOINTS	
Exploratory			
To document the presence of LMN-201 therapeutic proteins at the terminal ileum		Detect presence of LMN-201 therapeutic proteins (VHHs and lysin) in collected ileostomy fluid by EIA	
Exploratory			
To determine variability between individuals in the quantity of LMN-201 therapeutic proteins at the terminal ileum		Quantitate LMN-201 therapeutic proteins (VHHs and lysin) in collected ileostomy fluid by EIA	

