5. STUDY DESIGN

5.1 General Study Design

This is a Phase 1, multi-site, open label, nonrandomized, exploratory study to assess delivery of LMN-201 components via enteric capsules.

The trial will be evaluated through 2 cohorts of up to 6 subjects each. The first cohort will utilize specific components to allow analysis of individual component digestion. Eligible subjects with mature ileostomies will be consented, enrolled, assigned to treatment sequentially, and asked to swallow the following:

Subject	Number of capsules administered to subject—First cohort					
	Anti-toxin B VHH-1	Anti-toxin B VHH-2	Anti-toxin B VHH-3	Lysin capsules	Capsule with tube-shaped transit markers	Capsule with ring-shaped transit markers
1	3	—	—	1	1	1
2	3	—	—	1	1	1
3	—	3	—	1	1	1
4	—	3	—	1	1	1
5	—	—	3	1	1	1
6	—	—	3	1	1	1

Every hour after ingestion, ileostomy fluid will be collected, weighed, filtered, and analyzed for the presence of capsules and/or transit markers. This procedure will be repeated for four hours after the capsules and/or transit marker are observed in the ileostomy collection, or 12 hours after ingestion, whichever time is shorter.

The trial will be adapted between the first and the second cohort in the following manner:

- If intact enteric capsules are observed in the ileostomy fluid of more than one participant
 - And the transit time is less than 4 hours, then a fluid restriction to less than 150 ml per hour will be implemented for the second cohort.
 - And the transit time is greater than 4 hours, then immediate release capsules will be utilized for the second cohort.
- If the number of enteric capsules that remain encapsulated in the ileostomy fluid is less than 20%
 - Then the number of subjects in the second cohort will decrease to three.

The second cohort, allowing for the above changes, will utilize a ‘cocktail’ formulation of VHHS. Subjects will be asked to swallow the following:

Subject	Number of capsules administered to subject—Second cohort					
	Anti-toxin B VHH-1	Anti-toxin B VHH-2	Anti-toxin B VHH-3	Lysin capsules	Capsule with tube-shaped transit markers	Capsule with ring-shaped transit markers
1	1	1	1	1	1	1
2	1	1	1	1	1	1
3	1	1	1	1	1	1

Any changes not described above will only be implemented once a protocol amendment has been submitted to the appropriate Institutional Review Board (IRB) or Independent Ethics Committee (IEC), and has been reviewed and approved.

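### The primary objective is protein delivery to the terminal ileum, but the only primary endpoint is visual: it can show capsule opening and transit, not whether released protein survived

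*Protocol*

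**What the plan says.** The primary objective in protocol Section 4 is: "To determine if enteric coating on components of LMN-201 is sufficient to deliver therapeutic proteins to the terminal ileum". The synopsis (Section 1.1) has the same target and names the VHH proteins and lysin. Section 3.1 closes on the same question, whether "enteric capsules containing constituents of LMN-201 are sufficient to deliver therapeutic proteins to the terminal ileum".

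The one primary endpoint, identical in Section 4 and the synopsis, is "Presence or absence of capsules and/or transit markers in ileostomy fluid by visual observation". Protein appears only among the exploratory endpoints, as "Detect presence of LMN-201 therapeutic proteins (VHHs and lysin) in collected ileostomy fluid by EIA" and as quantitation by the same assay.

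The protocol also says why protein survival matters. Section 3.1 states that "digestion of the therapeutic is the functional equivalent to metabolism within the gastrointestinal (GI) tract and remains the most significant challenge", and that the biomolecules "need to be delivered, undigested, and in a fully functional form to the distal small bowel and large intestine to be effective". Section 5.1 adds: "The first cohort will utilize specific components to allow analysis of individual component digestion".

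One passage points the other way. The Study Design row of the synopsis describes the study as intended "to evaluate the function of enteric capsules on drug release", which fits a visual endpoint.

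**The concern.** A primary endpoint should be able to answer the primary objective, in a descriptive study as much as in a confirmatory one. Here the objective is about protein, and the endpoint is about capsules and plastic markers. The protocol's own rationale makes digestion of the protein the main uncertainty, and the endpoint is blind to it.

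The risk is in reporting. If free markers from the enteric marker capsule appear and no intact capsules are seen, the primary result will look favourable. It could then be read as showing that the proteins were delivered, when it shows only that capsules opened and passed.

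The and/or wording adds to this. An intact enteric capsule (not opened) and free markers from the enteric marker capsule (opened) point in opposite directions, yet each counts as presence. Immediate-release markers alone also count, although they say nothing about enteric function.

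**Working it through.** The protocol gives no figure to reproduce for this point. The check sets the texts side by side and then counts what a visual record leaves open.

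**1. What each visual item can show.** Section 8.1 has the material retained on the filter examined for intact capsules, remnants and markers. Section 9.2 gives the purpose of the markers as transit time and visible dissolution.

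| Item seen | Shows | Leaves open |
|---|---|---|
| Intact enteric capsule | That capsule did not open before the stoma | Fate of protein from the other capsules |
| Capsule remnant | A capsule opened | Whether its protein survived |
| Free markers from the enteric marker capsule | That capsule opened upstream of the stoma | Whether any drug protein survived |
| Immediate-release markers | Transit reference | Enteric function and protein |

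No row changes if the surviving fraction of released protein moves from 0% to 100%.

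**2. How many protein outcomes fit one visual record.** Inputs from the tables in Section 5.1: a first-cohort subject receives 2 proteins (one VHH in three capsules, lysin in one); a second-cohort subject receives 4 proteins (three VHHs and lysin, one capsule each). If all four drug capsules opened, each protein may be detected or not without changing the record:

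- patterns = 2^(number of proteins)
- first cohort: 2^2 = 4
- second cohort: 2^4 = 16

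**3. How many delivery questions the study poses.** One per subject and protein, at the planned maximum:

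- 6 × 2 + 6 × 4 = 12 + 24 = 36
- if the second cohort is reduced to three: 6 × 2 + 3 × 4 = 12 + 12 = 24

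Wherever the capsules have opened, the primary endpoint answers none of these.

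**4. What the EIA adds.** It responds to protein survival, within limits. In Section 8.1 the aliquots follow filtration, so the assay shows protein detectable in filtrate. It does not show function, site of release, protein still inside an intact capsule, or protein held on the filter.

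**5. What is not affected.** Section 11.2 states that no hypothesis is tested, so there is no error rate or power to distort. The adaptation rules in Section 5.1 use intact capsules and transit time, not protein, so they work as written whichever endpoint is primary.

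**The case against.** The best defence is that Section 4 divides the question on purpose: the primary objective concerns whether the coating suffices, and a separate exploratory objective, paired with the EIA, documents the protein. The Study Design row and Section 9.2 support a capsule-function reading, the EIA is planned on the same fluid, and without a hypothesis test the primary label carries little weight. Part of this stands: the data will exist, and the fault is one of ranking and wording. But the stated objective is sufficiency to deliver protein. That cannot be concluded without evidence that protein was there, and such evidence is left to the exploratory tier.

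A second objection is that promoting the EIA would still fall short of the functional standard in Section 3.1. That is correct, and it limits what the fix may claim.

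A third is that setting aside negative EIA results as not evaluable could inflate detection. As an assumed illustration, 6 positives of 12 is 50%, but if 4 negatives are reclassified and dropped it becomes 6/8 = 75%. This stands, and it is why the fix keeps all dosed subjects in the denominator.

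Four stronger readings are tempting but unsupported:

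- That the visual endpoint is uninformative. Sections 5.1, 8.1 and 9.2 let its items be read separately, and they then speak to opening and transit.
- That release before the terminal ileum is a failure the endpoint misses. Sections 3.1 and 9.4 say the capsules are designed to release at or before that point.
- That collection always stops four hours after the first item, so late enteric items are lost. Section 7.2 makes four additional hours a minimum, within the 12-hour limit.
- That the counts in step 2 extend simply to partly intact recoveries. They would depend on knowing which capsules were intact, and Section 9.4 describes the drug capsules as white and opaque.

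**Conclusion.** The mismatch is real and should be fixed. As written, the primary result can conclude that enteric capsules opened and passed; it cannot conclude that therapeutic protein was delivered. With all drug capsules open, one visual record is compatible with 4 protein patterns in a first-cohort subject and 16 in a second-cohort subject. At most 36 subject-protein questions (24 with the reduced second cohort) depend on an exploratory assay. These counts assume full enrolment and that any protein from an opened capsule may or may not be detectable.

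The consequence is limited to what the primary result may claim. A reader might infer that the trial cannot address delivery at all; the documents do not support that, since the EIA is planned on fluid from every timepoint. Nor would a positive EIA establish functional delivery.

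**What to change.** Amend Section 4 and the synopsis in one of two ways.

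**Option 1: keep the objective and bring the endpoint up to it.**
- Make EIA detection of each administered protein in filtrate, relative to the subject's own pre-dose fluid, co-primary with the visual endpoint. Move the matching exploratory objective up with it and leave quantitation exploratory.
- Split the visual endpoint into intact enteric capsules, capsule remnants, enteric-capsule markers, and immediate-release markers as transit reference only.
- Report by protein and cohort over all dosed subjects, showing the counts detected, not detected and not evaluable, with the last class defined in advance. Word a negative as not detected in filtrate, not as digested.
- Rest conclusions on opening on the visual components and conclusions on delivery on the EIA. Draw conclusions on enteric delivery only from subjects given the drug in enteric capsules. If the second cohort is switched to immediate-release capsules, as Sections 5.1 and 9.4 allow, report it separately.

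**Option 2: keep the endpoint and narrow the objective.** Restate the primary objective as enteric capsule opening and transit, in line with the Study Design row of the synopsis, and draw no primary conclusion on protein delivery.

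Option 1 needs no new samples: Section 8.1 already provides pre-dose fluid, a spiked positive control and one shipped tube per timepoint. Its price is that the primary result waits for the EIA and may look less favourable. Option 2 costs only wording but gives up the primary conclusion that the protocol sets out to reach.

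Under either option the marker descriptions must be reconciled. The synopsis puts ring-shaped markers in the enteric capsule and tube-shaped ones in the immediate-release capsule; Sections 9.1 and 9.2 have the reverse. Until this is settled, the enteric marker component cannot be read.
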